11.2 CLINICAL LABORATORY PARAMETERS

Descriptive statistics for clinical laboratory values (in International System of units [SI]) at baseline, postbaseline, and changes from baseline values at each postbaseline timepoint will be presented by treatment group for the following laboratory parameters:

Hematology: Hemoglobin, hematocrit, red blood cell count, red blood cell indices (mean corpuscular volume, mean corpuscular hemoglobin, mean corpuscular hemoglobin concentration), white blood cell count, white blood cell count differential (neutrophils, lymphocytes, monocytes, eosinophils, and basophils), and platelet count

Chemistry: Sodium, potassium, chloride, bicarbonate, glucose, blood urea nitrogen, creatinine, total bilirubin, alkaline phosphatase, aspartate aminotransferase, alanine aminotransferase, lactate dehydrogenase, creatine kinase, total protein, albumin, calcium, phosphorus, uric acid, total cholesterol, estimated glomerular filtration rate

Urinalysis: Specific gravity, pH

In addition, descriptive statistics for values and changes from the baseline values in conventional units at each assessment time point will be presented for selected clinical laboratory parameters listed in Appendix 20.1. A description of reporting the lab values in conventional units in participant narratives (along with the standard reporting in SI units) is presented at the end of Appendix 0.

Clinical laboratory test values will be considered potentially clinically significant (PCS) if they meet either the lower-limit or higher-limit PCS criteria listed in Table 11.2-1. The number and percentage of participants who have PCS postbaseline clinical laboratory values will be tabulated by treatment group. The percentages will be calculated relative to the number of participants with available non-PCS baseline values and at least 1 postbaseline assessment for the double-blind

treatment period. The numerator will be the total number of participants with available non-PCS baseline values and at least 1 PCS postbaseline value during the study. A supportive tabular display of participants with PCS postbaseline values will be provided, including the participant identification (PID) number, baseline and all postbaseline (including non-PCS) values.

In addition, a tabular display showing all AEs that occurred in participants who had PCS postbaseline clinical laboratory values will be provided.

Shift tables from baseline to end of double-blind treatment period for clinical laboratory parameters will be presented by treatment group for the following categories: low, normal, and high, which are provided by lab vendor.

Participants who meet the potential Hy's Law criteria from the first dose of study drug to the end of study will be summarized. Supportive tabular displays will also be provided.

Table 11.2-1. Criteria for Potentially Clinically Significant Laboratory Results

Parameter	SI Unit	Lower Limit	Higher Limit
CHEMISTRY			
Albumin	g/L	< 0.8 × LLN	> 1.2 × ULN
Alanine aminotransferase	U/L	—	≥ 3.0 × ULN
Alkaline phosphatase	U/L	—	≥ 3.0 × ULN
Aspartate aminotransferase	U/L	—	≥ 3.0 × ULN
Bicarbonate	mmol/L	< 0.9 × LLN	> 1.1 × ULN
Bilirubin, total	μmol/L	—	≥ 1.5 × ULN
Blood urea nitrogen	mmol/L	—	> 1.5 × ULN
Calcium	mmol/L	< 0.9 × LLN	> 1.1 × ULN
Chloride	mmol/L	< 0.9 × LLN	> 1.1 × ULN
Cholesterol, total	mmol/L	—	> 1.6 × ULN
Creatinine	μmol/L	—	> 1.5 × ULN
Creatine kinase	U/L	—	> 2.0 × ULN
Estimated glomerular filtration rate	mL/min/1.73m ²	<60 mL/min/1.73m ²	—
Glucose, nonfasting	mmol/L	< 0.8 × LLN	> 2.0 × ULN
Lactate dehydrogenase (LDH)	U/L	—	> 3.0 × ULN
Phosphorus	mmol/L	< 0.9 × LLN	> 1.1 × ULN
Potassium	mmol/L	< 0.9 × LLN	> 1.1 × ULN
Protein, total	g/L	< 0.9 × LLN	> 1.1 × ULN
Sodium	mmol/L	< 0.9 × LLN	> 1.1 × ULN
Uric acid	μmol/L	—	> 1.2 × ULN
HEMATOLOGY			
Basophils, absolute cell count	10 ⁹ /L	—	> 2.0 × ULN
Eosinophils, absolute cell count	10 ⁹ /L	—	> 2.0 × ULN
Hematocrit	Ratio	< 0.9 × LLN	> 1.1 × ULN
Hemoglobin	g/L	< 0.9 × LLN	> 1.1 × ULN
Lymphocytes, absolute cell count	10 ⁹ /L	< 0.7 × LLN	> 1.3 × ULN
Monocytes, absolute cell count	10 ⁹ /L	< 0.5 × LLN	> 2.0 × ULN
Neutrophils, absolute cell count	10 ⁹ /L	< 0.7 × LLN	> 1.3 × ULN
Platelet count	10 ⁹ /L	< 0.5 × LLN	> 1.5 × ULN
Red blood cell count	10 ¹² /L	< 0.9 × LLN	> 1.1 × ULN
White blood cell count	10 ⁹ /L	< 0.9 × LLN	> 1.5 × ULN
URINALYSIS			
pH	pH	< 0.9 × LLN	> 1.1 × ULN
Glucose	—	—	At least 1+
Protein	—	—	At least 1+
Specific gravity	—	—	> 1.1 × ULN

LLN = lower limit of normal value; ULN = upper limit of normal value; normal value provided by laboratory.

SI = Le Système International d'Unités (International System of Units).

The number and percentage of participants meeting each of the following criteria for postbaseline hepatic laboratory abnormalities listed in [Table 11.2-2](#) will be summarized by treatment group. The percentages will be calculated relative to the number of participants with at least 1 available postbaseline assessment. The numerator will be the total number of participants having at least 1 postbaseline value that meets the specific category during the study. A supportive listing will also be provided.

Table 11.2-2. Criteria for Hepatic Laboratory Abnormalities

Laboratory Parameter	Categories
ALT	$\geq 1 \times \text{ULN}$
	$\geq 1.5 \times \text{ULN}$
	$\geq 2 \times \text{ULN}$
	$\geq 3 \times \text{ULN}$
	$\geq 5 \times \text{ULN}$
	$\geq 10 \times \text{ULN}$
	$\geq 20 \times \text{ULN}$
AST	$\geq 1 \times \text{ULN}$
	$\geq 1.5 \times \text{ULN}$
	$\geq 2 \times \text{ULN}$
	$\geq 3 \times \text{ULN}$
	$\geq 5 \times \text{ULN}$
	$\geq 10 \times \text{ULN}$
	$\geq 20 \times \text{ULN}$
ALT or AST	$\geq 1 \times \text{ULN}$
	$\geq 1.5 \times \text{ULN}$
	$\geq 2 \times \text{ULN}$
	$\geq 3 \times \text{ULN}$
	$\geq 5 \times \text{ULN}$
	$\geq 10 \times \text{ULN}$
	$\geq 20 \times \text{ULN}$
Bilirubin Total	$\geq 1 \times \text{ULN}$
	$\geq 1.5 \times \text{ULN}$
	$\geq 2 \times \text{ULN}$
	$\geq 3 \times \text{ULN}$
	$\geq 5 \times \text{ULN}$
	$\geq 10 \times \text{ULN}$
	$\geq 20 \times \text{ULN}$
Alkaline Phosphatase	$\geq 1 \times \text{ULN}$
	$\geq 1.5 \times \text{ULN}$
	$\geq 2 \times \text{ULN}$
	$\geq 3 \times \text{ULN}$
	$\geq 5 \times \text{ULN}$
	$\geq 10 \times \text{ULN}$
	$\geq 20 \times \text{ULN}$
Concurrent Elevations ¹	ALT or AST $\geq 3 \times \text{ULN}$ and Bilirubin Total $\geq 1.5 \times \text{ULN}$
	ALT or AST $\geq 3 \times \text{ULN}$ and Bilirubin Total $\geq 2 \times \text{ULN}$
Potential Hy's Law ¹	ALT or AST $\geq 3 \times \text{ULN}$ and Bilirubin Total $\geq 2 \times \text{ULN}$ and ALP $< 2 \times \text{ULN}$

ALT = alanine aminotransferase; AST = aspartate aminotransferase; TBL = total bilirubin; ALP = alkaline phosphatase; ULN = upper limit of normal (value provided by the laboratory).

¹ Elevations are from the same day

The number and percentage of participants with an adjudicated case (i.e., $ALT \geq 3 \times ULN$ and/or $AST \geq 3 \times ULN$) will be summarized by treatment group and by relationship of ALT or AST elevation to study medication. The percentages will be calculated relative to the number of participants with at least 1 adjudicated case. The numerator will be the number of participants with at least 1 adjudicated case in the specific category of relationship. If a participant has more than 1 adjudicated case, he or she will be counted in the most relevant category of relationship.

Participants with an adjudicated case (i.e. $ALT \geq 3 \times ULN$ or $AST \geq 3 \times ULN$) will be listed with their ALT and AST assessments, adjudication dates, relationship of ALT or AST elevation to study medication, and confounding factor(s). Additional listings will be provided for participants who meet $ALT \geq 3 \times ULN$ or $AST \geq 3 \times ULN$ and/or potential Hy's law and have one of the following categories: at least 1 abnormal liver biochemistry risk factor, at least 1 liver disease sign and symptom, at least 1 liver diagnostic test performed, consultation with a specialist for liver evaluation, liver lab tests performed, and drug screen performed, respectively.

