- ^f Clinical laboratory determinations include chemistry, hematology, INR, and urinalysis to be collected for all visits. Samples for serology and the urine drug screen will be collected only at screening (Visit 1).
- ^g PK sample should be collected prior to the first dose at Visit 2. One sample should be collected prior to the morning dose during one of the Visits 3 to 7, and the remaining samples should be collected 1 to 10 hours postdose.
- ^h Participant should begin using the eDiary as soon as it is dispensed. If it is subsequently determined that the participant has failed entry criteria, the eDiary should be returned to the site.
- ⁱ Participants must bring the eDiary to visits and review with coordinators.
- ^j Clinicians will complete on eTablet. The screening/baseline assessment of the C-SSRS will be completed. At all other visits, the ‘Since Last Visit’ C-SSRS will be completed.
- ^k Participant will complete on eTablet.
- ^l PRO measures should be administered prior to any tests and/or evaluations unless indicated otherwise in the protocol (eg, during Randomization Visit 2, some tests will be conducted prior to the PROs for eligibility).
- ^m EQ-5D-5L will be given on eDiary during 7 days in the baseline period and during specific time periods for Visit 1 to 7, except at Visit 8 (Week 16) where it will be administered on an eTablet.
- ⁿ eDiary will be collected on Visit 2 for screen failures.
- ^o Collected at Visit 7/ET only for participants who complete the double-blind treatment period.
- ^p Collected at Visit 8/Follow-up only for participants who discontinue from the double-blind treatment period.
- ^q The first dose of study intervention should be taken at the study site.

1. Background and Clinical Rationale

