1.2 Overview of Atogepant

Atogepant is a potent, selective oral CGRP receptor antagonist being developed for migraine prevention. CGRP is a neuropeptide implicated in the pathophysiology of migraine. CGRP levels in the cranial venous outflow (ie, external jugular vein) are increased during a migraine attack and exogenously administered CGRP has been shown to trigger migraine-like headache in patients with migraine. The majority (80% to 90%) of trigeminal A δ fibers that innervate the dura contain CGRP, suggesting that these fibers may be involved in sterile neurogenic inflammation and migraine pain transmission. Furthermore, the CGRP receptor is present on human meningeal and cerebral blood vessels. These observations suggest that activation of the trigeminovascular system, with release of CGRP, may play a key role in migraine pathogenesis and that inhibition of CGRP may yield a novel therapeutic approach to treating migraine.

The ability of CGRP inhibition to induce pain relief in the acute treatment of migraine was initially observed with an IV formulation of olcegepant ([Olesen 2004](#)) and replicated by Merck & Co., Inc. with an oral formulation of MK-0974 (telcagepant), a highly selective CGRP receptor antagonist. In Phase 3 studies, telcagepant was superior to placebo in the primary endpoints of 2-hour pain freedom, 2-hour pain relief, and the absence of associated symptoms (photophobia, phonophobia, and nausea), as well as the key secondary endpoint of 24-hour sustained pain freedom ([Connor 2009](#)). However, serum ALT increases were observed with telcagepant. For this reason, the development of these oral CGRP antagonists was stopped.

A Phase 2/3 clinical study (Study CGP-MD-01) was conducted, which compared atogepant 10 mg once daily, atogepant 30 mg once daily, atogepant 30 mg BID, atogepant 60 mg once daily and atogepant 60 mg BID to placebo in EM prevention. Overall, all the atogepant doses tested were well tolerated and the AE profile of all atogepant doses did not significantly differ from placebo. For the primary efficacy endpoint of change from baseline in mean monthly migraine days across the 12-week treatment period, all atogepant doses demonstrated a statistically significant reduction compared to placebo in patients with EM.

Additional information on nonclinical pharmacology, toxicology, and PK properties of atogepant can be found in the investigator's brochure.

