6.5.3 Clinical Laboratory Determinations

Blood and urine samples for clinical laboratory tests will be collected at the visits outlined in Table 1. Hematology, chemistry, coagulation parameters (INR), and urinalysis will be conducted at these visits. Serology and the urine drug screen will be conducted at screening (Visit 1). The investigator will assess the clinical significance of any values outside the reference ranges provided by the central laboratory. Participants with abnormalities judged to be clinically significant laboratory values that meet exclusionary criteria, or positive results on the urine drug screen at screening (Visit 1), will be excluded from the study.

Women of childbearing potential will be required to have a urine pregnancy test at all visits. A positive pregnancy test at Visit 1 or Visit 2 will exclude the participant from the study.

Investigators may also perform unscheduled clinical laboratory determinations at any time for the purpose of participant safety.

Participants are not required to fast overnight before coming in for their appointments.

The clinical laboratory parameters to be measured are shown in Table 3.

Table 3 Clinical Laboratory Parameters

Category	Parameter
Chemistry	Sodium, potassium, chloride, bicarbonate, glucose, blood urea nitrogen, creatinine, total bilirubin, alkaline phosphatase, aspartate aminotransferase, alanine aminotransferase, lactate dehydrogenase, creatine kinase, total protein, albumin, calcium, phosphorus, uric acid, total cholesterol. The estimated glomerular filtration rate will be calculated by the central laboratory
Hematology	Hemoglobin; hematocrit; red blood cell count; red blood cell indices (mean corpuscular volume, mean corpuscular hemoglobin, mean corpuscular hemoglobin concentration); white blood cell count including differential (neutrophils, lymphocytes, monocytes, eosinophils, and basophils); platelet count
Urinalysis	Urine dipstick for specific gravity, pH, protein, glucose, ketones, bilirubin, and blood; microscopic exam including red blood cells/high-power field, white blood cells/high-power field, and casts/low-power field
Coagulation	International normalized ratio
Serology	At Visit 1 only: anti-hepatitis A IgM antibody, hepatitis B surface antigen, anti-hepatitis C antibody, anti-hepatitis E IgM antibody

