9.5 ALT or AST Elevations

A treatment-emergent ALT $\geq 3 \times$ ULN and/or AST $\geq 3 \times$ ULN is considered an AE of special interest. Any participant with this laboratory result after study intervention was taken must have repeat testing within 48 to 72 hours to confirm the abnormality. For this repeat testing, the following laboratory tests must be drawn: hematology and chemistry panels, INR, serum acetaminophen level, urine drugs of abuse screen, and blood alcohol level. An extra blood serology sample must be collected and sent to the central laboratory for further diagnostic testing, at a later date, if needed. In addition, the investigator will perform a complete history and examination to evaluate the participant for possible liver disease.

All AEs of special interest must be reported to the sponsor within 24 hours of the time the investigator becomes aware of the event using the abnormal liver function reporting form and the AE eCRF. All new elements of history, physical examination, diagnostic testing results, and other relevant medical reports are to be reported for each AE of special interest.

If an ALT or AST $\geq 3 \times$ ULN is confirmed, close medical follow-up is required:

For these participants, the following laboratory tests must be performed: anti-hepatitis A IgM, hepatitis B surface antigen, anti-hepatitis B core IgM, hepatitis C antibody, hepatitis C quantitative RNA by polymerase chain reaction, anti-hepatitis E IgM, anti-hepatitis E IgG, Cytomegalovirus IgM antibody, and Epstein-Barr Virus IgM antibody. The participant must be followed clinically and further medical evaluation (for other causes of acute hepatic injury) should be done per the judgment of the investigator and in conjunction with medical personnel at the sponsor. In general, the chemistry panel should be repeated 1 to 2 times per week to follow the course of ALT/AST elevation.

Study intervention must be discontinued if any of the following criteria are met:

- ALT or AST $\geq 3 \times$ ULN and the participant is symptomatic with the appearance of fatigue, nausea, vomiting, right upper quadrant pain or tenderness, fever, rash, or eosinophilia ($> 5\%$)
- ALT or AST $\geq 3 \times$ ULN and total bilirubin $> 2 \times$ ULN
- ALT or AST $\geq 3 \times$ ULN and INR > 1.5
- ALT or AST $\geq 5 \times$ ULN for more than 2 weeks
- ALT or AST $\geq 8 \times$ ULN

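### INR is scheduled at every visit and is part of one mandatory liver-stop criterion, but SAP 11.2 names it in no list or table, so that criterion is not counted by arm

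*SAP*

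**What the plan says.** **Collection.** Footnote f of Protocol Table 1 reads "Clinical laboratory determinations include chemistry, hematology, INR, and urinalysis to be collected for all visits", and the SAP repeats it under its own schedule (Table 4-1). Protocol 6.5.3 says "coagulation parameters (INR), and urinalysis will be conducted at these visits", and Protocol Table 3 gives INR its own Coagulation category, apart from chemistry and hematology.

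**Use.** Protocol 9.5 states "Study intervention must be discontinued if any of the following criteria are met" and gives five criteria. One pairs ALT or AST at or above 3 x ULN with INR; its text ends "ULN and INR > 1.5". INR is also among the tests required when such an elevation is repeated for confirmation.

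**Analysis.** SAP 11.2 provides four kinds of by-arm output that matter here:
- Descriptive statistics that "will be presented by treatment group for the following laboratory parameters", followed by named entries under Hematology, Chemistry and Urinalysis.
- Counts of potentially clinically significant values, using the thresholds in Table 11.2-1, which has the same three groups.
- "The number and percentage of participants meeting each of the following criteria for postbaseline hepatic laboratory abnormalities listed in" Table 11.2-2. This covers ALT, AST, ALT or AST, bilirubin and ALP at seven multiples of ULN, two concurrent ALT/AST-with-bilirubin rows and a potential Hy's law row.
- Low/normal/high shift tables from baseline to the end of double-blind treatment, with no parameters named, and a summary of adjudicated ALT/AST cases.

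**The concern.** Safety and tolerability form a stated objective, and the protocol treats the liver as a monitored risk. On an earlier oral drug of the same class it records: "However, serum ALT increases were observed with telcagepant". ALT or AST at or above 3 x ULN is an adverse event of special interest, with its own adjudication committee. The protocol uses INR to turn such an elevation into a mandatory stop, yet the SAP's laboratory section does not mention INR at all. If the SAP is followed as written, a reader of the study report would see no INR descriptive statistics by arm. Nor could that reader tell how many participants in each arm met the ALT/AST-with-INR criterion.

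**Working it through.** The plan states no figure to reproduce, so the check sets the protocol's stop criteria beside the SAP's by-arm output.

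**Step 1. Where INR appears in the SAP.** It appears in the abbreviation list and the schedule of activities (Table 4-1 and its notes). It does not appear in the SAP 11.2 descriptive list, Table 11.2-1 or Table 11.2-2.

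**Step 2. The five Protocol 9.5 criteria against Table 11.2-2.**

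| Protocol 9.5 criterion | Nearest by-arm row | Match |
|---|---|---|
| ALT/AST >= 3 x ULN with listed symptoms or eosinophilia | >= 3 x ULN | Enzyme part only |
| ALT/AST >= 3 x ULN, bilirubin > 2 x ULN | Concurrent row, bilirubin >= 2 x ULN | Near match |
| ALT/AST >= 3 x ULN, INR > 1.5 | >= 3 x ULN | Enzyme part only; INR nowhere |
| ALT/AST >= 5 x ULN for more than 2 weeks | >= 5 x ULN | No duration |
| ALT/AST >= 8 x ULN | >= 5 and >= 10 x ULN | Values from 8 to below 10 cannot be separated from 5 to below 8 |

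**Step 3. What the existing rows say about the INR criterion.** Anyone who meets it has ALT or AST >= 3 x ULN. So, in each arm,

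n(ALT/AST >= 3 x ULN and INR > 1.5) <= n(ALT/AST >= 3 x ULN).

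The planned row gives an upper bound on the number meeting the criterion, but not the number itself.

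**Step 4. Whether the shift tables close the gap.** Suppose they include INR. They place each participant in the laboratory vendor's low, normal or high category at baseline and at the end of treatment. That does not use the 1.5 cut-off, misses a rise that resolves before the end of treatment, and does not link INR to ALT or AST.

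**Step 5. Volume of data.** Clinical laboratory tests are scheduled at six post-baseline visits (Visits 3 to 8) for about 750 participants: 6 x 750 = 4,500 INR values. If every participant rolled over to an extension study and skipped Visit 8, the figure is 5 x 750 = 3,750. Both are ceilings before dropout and missed or remote visits. They count routine draws, not affected participants.

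**The case against.** The strongest reply is that core hepatic reporting is already in place. All five stop criteria require ALT or AST at or above 3 x ULN, so every stop case under them lies inside a row reported by arm. Such cases are adjudicated and summarised by arm and by relationship to study medication. Both hepatic events of special interest, ALT/AST >= 3 x ULN and potential Hy's law, have their own rows. Individual values appear in listings, and adverse events leading to discontinuation are tabulated by arm. Protocol 9.5 is a participant-management rule, and neither document obliges the SAP to tabulate each stop criterion. Table specifications sit in a separate document, which might add INR.

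Most of this stands, and it limits the point. It does not remove it. The adjudication summary does not classify by INR, listings give no counts by arm, and the discontinuation tables report event terms rather than which criterion was met. Protocol 7.3.4 includes clinical laboratory evaluations in the safety analysis without excepting INR. SAP Section 18 records only the addition of health outcome endpoints as a change from the protocol. Nothing therefore indicates that INR was left out on purpose.

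A reader might infer that no by-arm table could contain INR. The unnamed shift-table parameters make that too strong. A reader might also point to INR's absence from the conventional-units list (SAP Table 20.1-1), but INR is a unitless ratio, so that absence shows nothing.

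**Conclusion.** The point holds as a limited reporting gap. INR has no named descriptive summary or abnormality row, and one of the protocol's five mandatory-stop criteria cannot be counted by arm from the planned tables. At most 4,500 scheduled post-baseline values are involved. The number of participants who would meet the joint criterion cannot be derived from the documents. No efficacy estimate, test or core hepatic table is affected.

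A reader might go further and conclude that the trial's main anticipated harm is incompletely reported, or that liver-safety analysis is missing. The documents do not support that. Core liver outputs are planned by arm, the ALT signal cited is for another drug, the protocol reports no safety concerns to date for atogepant, and suicidality is also an event of special interest. Nor do the documents require a row for each stop criterion. The 8 x ULN gap is a matter of granularity, and INR > 1.5 has standing in Protocol 9.5 only jointly with ALT or AST.

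The conclusion assumes that the parameters named in SAP 11.2 define the planned output. The separate table specifications were not available and could already include INR.

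**What to change.** In SAP 11.2:
1. Add a Coagulation entry (INR) to the parameters summarised by visit and arm.
2. State that the shift tables include INR.
3. Add to Table 11.2-2 the concurrent row *ALT or AST >= 3 x ULN and INR > 1.5*, taken unchanged from Protocol 9.5 and read with that table's existing same-day footnote.

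A >= 8 x ULN row for ALT, AST, and ALT or AST is optional.

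These changes concern reporting only. They alter no stopping rule or clinical threshold, need no new data and add no hypothesis test. The cost is a few lines of SAP text and slightly longer safety output.

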11.3 VITAL SIGNS

Descriptive statistics for vital signs (systolic and diastolic blood pressures [sitting and standing], pulse rate [sitting and standing], respiratory rate, temperature, weight, orthostatic systolic blood pressure, orthostatic diastolic blood pressure, and orthostatic pulse rate) values at baseline, postbaseline, and changes from baseline values at each postbaseline timepoint will be presented by treatment group. Orthostatic vital sign values (orthostatic systolic and diastolic blood pressures, and orthostatic pulse rate) are defined as the corresponding standing measurement minus sitting measurement of systolic and diastolic blood pressures and pulse rate respectively.

Vital sign values will be considered PCS if they meet both the observed-value criterion and the change-from-baseline-value criterion, if both criteria are available, or meet either the observed-value criterion or the change-from-baseline-value criterion as listed in [Table 11.3-1](#). The number and percentage of participants who have PCS postbaseline vital sign values will be tabulated by study treatment. The percentages will be calculated relative to the number of participants who have available baseline or non-PCS baseline (for parameters with only the observed value criterion) values and at least 1 postbaseline assessment. The numerator will be the total number of participants with at least 1 PCS postbaseline value during the study. A supportive listing of

participants with PCS postbaseline values will be provided. In addition, a tabular display showing all AEs that occurred in participants who had PCS postbaseline vital sign values will be provided.

Table 11.3-1. Criteria for Potentially Clinically Significant Vital Signs

Parameter	Flag	Criteria	
		Observed Value	Change from Baseline
Systolic blood pressure, mm Hg	High	≥ 180	Increase of ≥ 20
	Low	≤ 90	Decrease of ≥ 20
Diastolic blood pressure, mm Hg	High	≥ 105	Increase of ≥ 15
	Low	≤ 50	Decrease of ≥ 15
Pulse rate, bpm	High	≥ 120	Increase of ≥ 15
	Low	≤ 50	Decrease of ≥ 15
Weight, kg	High	—	Increase of $\geq 7\%$
	Low	—	Decrease of $\geq 7\%$
Orthostatic SBP change, mm Hg	Low	≤ -20	—
Orthostatic DBP change, mm Hg	Low	≤ -15	—
Orthostatic Pulse rate change, bpm	High	≥ 25	—

SBP = Systolic blood pressure, DBP = Diastolic blood pressure, bpm = beats per minute.

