End of Double-blind Treatment Period is defined as the last available assessment during double-blind treatment period. End of Double-blind Treatment Period results will be presented in analysis tables for clinical laboratory values and vital signs.

End of Study is defined as the last available assessment during the study, including double-blind and safety follow-up period.

End of Study results will be presented in analysis tables for safety parameters, including but not limited to electrocardiograms, clinical laboratory values, and vital signs.

ET = early termination.

For endpoints collected by visit (not for eDiary data), if a participant has 2 or more visits within the same window, the last visit with a non-missing value will be used for analysis, unless specified otherwise.

The following algorithm is used to define the double-blind treatment period and the follow-up periods unless specified otherwise. The double-blind treatment period starts with the date of the first dose of double-blind study treatment and ends with the latest date of the last study medication date, and the last scheduled assessment date of Visit 2 to Visit 7 for participants who entered the safety follow-up period; or ends with the latest date of the last study medication date, and last assessment date for participants who did not enter the safety follow-up period. The safety follow-up period starts with the 1 day after the end of the double-blind period and ends with the last scheduled assessment date of Visit 8 for participants who entered the estimand follow-up period;

or ends with the last assessment date for participants who did not enter the estimand follow-up period. The estimand follow-up period starts with the 1 day after the end of the safety follow-up period and ends with the last assessment date for participants who entered the estimand follow-up period.

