16.3 REPEATED OR UNSCHEDULED ASSESSMENTS OF SAFETY PARAMETERS

If a participant has repeated assessments before the start of the first treatment, the results from the final nonmissing assessment made prior to the start of the study treatment will be used as baseline. If a participant has 2 or more visits within the same window, the last visit with a nonmissing value will be used for summary over time. If end-of-study assessments are repeated or if unscheduled visits occur, the last nonmissing postbaseline assessment will be used as the end-of-study assessment for generating summary statistics. However, all postbaseline assessments will be used for PCS value determinations, and all assessments will be presented in the data listings.

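### Two PCS percentages in SAP 11.2 (laboratory) and 11.3 (orthostatic vital signs) have numerators that are not subsets of their denominators and can read too high

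*SAP*

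**What the plan says.** **Laboratory values (SAP 11.2).** The table is described this way: "The number and percentage of participants who have PCS postbaseline clinical laboratory values will be tabulated by treatment group". The denominator is the "number of participants with available non-PCS baseline values and at least 1 postbaseline assessment for the double-blind" treatment period. The numerator follows: "The numerator will be the total number of participants with available non-PCS baseline values and at least 1 PCS postbaseline value during the study".

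**Vital signs (SAP 11.3).** The denominator is participants with "available baseline or non-PCS baseline (for parameters with only the observed value criterion) values and at least 1 postbaseline assessment". The numerator is: "The numerator will be the total number of participants with at least 1 PCS postbaseline value during the study". In Table 11.3-1 only the three orthostatic changes (systolic pressure, diastolic pressure, pulse rate) have an observed-value criterion and no change-from-baseline criterion, so the non-PCS-baseline condition applies to them alone.

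**Time scope.** SAP 16.1 states: "End of Study is defined as the last available assessment during the study, including double-blind and safety follow-up period". It also states: "The safety follow-up period starts with the 1 day after the end of the double-blind period". SAP 16.3 adds that "all postbaseline assessments will be used for PCS value determinations". Protocol 8.4.3.1 collects laboratory samples and vital signs at Visit 8.

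**Comparator.** SAP 11.4 (ECG) puts the non-PCS-baseline condition in both numerator and denominator and limits neither to the double-blind period.

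**The concern.** A percentage described as the share of eligible participants who had an event needs every counted participant to be eligible. Two rules break this, by different routes.

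- In 11.3, the orthostatic denominator removes participants who already met the criterion before dosing, so that the table shows new abnormalities. The numerator lets them back in.
- In 11.2, the baseline condition matches on both sides but the time window does not. A PCS value found only at Visit 8, about four weeks after the last dose, counts against a denominator defined by the double-blind period.

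At stake are descriptive safety percentages in a pivotal trial. Two programmers, one reading the text literally and one working by analogy with 11.4, would produce different tables from the same data.

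**Working it through.** The SAP states no PCS rate, so there is no plan figure to reproduce. The check compares sets of participants; the arithmetic after it is illustration only.

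**Step 1: baseline condition.**

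| Section | In denominator | In numerator |
|---|---|---|
| 11.2 laboratory | non-PCS baseline | non-PCS baseline |
| 11.3 orthostatic | non-PCS baseline | none |
| 11.4 ECG | non-PCS baseline | non-PCS baseline |

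Only 11.3 fails. A participant who is PCS at baseline and again after baseline is counted above the line and excluded below it. Sitting and standing pressure and pulse escape this: they must also meet a change criterion, and their denominator needs only an available baseline.

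**Step 2: time window.**

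| Section | In denominator | In numerator |
|---|---|---|
| 11.2 laboratory | double-blind period | whole study |
| 11.3 vital signs | any postbaseline | whole study |
| 11.4 ECG | any postbaseline | whole study |

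Only 11.2 fails. Two kinds of participant are affected:

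- (a) no double-blind laboratory value, PCS at Visit 8: in the numerator only, so the subset property is broken;
- (b) double-blind values all non-PCS, first PCS value at Visit 8: in both sets, so the ratio is a proper proportion, but it mixes two windows.

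**Step 3: orthostatic illustration (all rates assumed).** Let b be the share PCS at baseline, r the share of those who are PCS again, and i the incidence among the rest.

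As written = [i(1 − b) + r·b] / (1 − b) = i + r·b/(1 − b). With matched sets it is i.

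- i = 5%, b = 1%, r = 30%: 5% + 0.003/0.99 = 5.3%, excess 0.3 points.
- i = 5%, b = 5%, r = 50%: 5% + 0.025/0.95 = 7.6%, excess 2.6 points.
- i = 5%, b = 10%, r = 80%: 5% + 0.08/0.90 = 13.9%, excess 8.9 points.

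**Step 4: laboratory illustration (all rates assumed).** The excess depends on which window is intended.

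- *Whole study intended.* Only (a) matters. Of 250 participants, suppose m = 5 have only a follow-up value and k = 1 of them is PCS, with 3% PCS among the other 245 (7.35 expected). As written: (7.35 + 1)/245 = 3.41%. Matched: 8.35/250 = 3.34%. Excess 0.07 points.
- *Double-blind intended.* Suppose everyone has a double-blind value, so only (b) matters. With double-blind rate i, share f with Visit 8 laboratory values and share q newly PCS there, as written = i + (1 − i)·f·q. For i = 3%, f = 20% and q = 0.5% this is 3.1%; for f = 100% and q = 2% it is 4.9%. Excess 0.1 to 1.9 points.

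**Step 5: direction.** Each mismatch adds to the numerator or shrinks the denominator, never the reverse. The percentage is too high or unchanged.

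**The case against.** The strongest reply is that counting Visit 8 is deliberate. SAP 16.3 uses every postbaseline assessment for PCS determination; the hepatic table in 11.2, the vital signs in 11.3 and the ECGs in 11.4 all use a whole-study numerator; potential Hy's Law cases run to the end of the study; and the TEAE window in 11.1 extends past the last dose. On that reading the stray text is the double-blind phrase in one denominator. This stands, and it decides which laboratory repair is the more natural.

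It also stands that case (a) should be rare. Laboratory samples are scheduled at every visit, Visit 3 or Visit 4 must be in office (Protocol 12.4), early-termination samples fall in the double-blind period under the SAP 16.1 algorithm, and rollover participants need no Visit 8. The case is not impossible: the remote schedule has no laboratory row, and missed samples move to the next in-person visit, which can be Visit 8.

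The tables are descriptive, the rule is the same in every arm, and the supporting displays let a reader look at individual participants. Table specifications sit in a separate document (SAP 4.0) and may already use matched sets. That limits the consequence but does not correct the SAP text, and none of it answers the orthostatic mismatch, which no convention elsewhere in the SAP supports.

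A reader might infer that off-drug and baseline-abnormal values together inflate the trial's on-treatment abnormality rates. The documents do not support that. The SAP calls these postbaseline percentages, not on-treatment rates. Baseline-abnormal participants cannot enter the laboratory numerator, and off-drug values create no mismatch in vital signs because neither side there is limited to treatment.

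**Conclusion.** Both rules are wrong as written. The orthostatic rule in 11.3 is the clearer error: its numerator admits participants whom its denominator excludes. The laboratory rule in 11.2 pairs two windows; if the whole study is intended, as 16.3 suggests, the numerical effect is probably very small.

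The reported percentages can be too high in any arm, placebo included. By how much cannot be computed, because the documents give neither the share PCS at baseline, nor how often those participants are PCS again, nor the share first PCS at Visit 8. The ranges above (0.3 to 8.9 points for orthostatic values; 0.07 points, or 0.1 to 1.9 points, for laboratory values according to the intended window) rest wholly on assumed rates and are not estimates for this trial. The effect on the contrast between arms is not determined, and no efficacy result is touched.

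**What to change.** **SAP 11.3.** Add to the numerator the condition that the participant had a non-PCS baseline, for those parameters judged on the observed value alone. Sections 11.2 and 11.4 already carry a baseline condition in their numerators.

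**SAP 11.2.** Use one window in both sentences. The repair most consistent with 16.3, 11.3 and 11.4 is to remove the double-blind restriction from the denominator, so that any postbaseline assessment qualifies. The alternative is to use the double-blind period on both sides, report follow-up separately among participants with a follow-up value, and amend 16.3 to match.

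**Cost.** One clause in 11.3 and one phrase in 11.2, with the table specifications checked against them. The alternative laboratory repair also needs a follow-up row and the change to 16.3. Neither needs new data.
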